3 STUDY POPULATION

This study will be conducted at the study sites listed in the Schema and in Section 2.2, among women who meet the eligibility criteria listed in Sections 3.1, 3.2, and 3.4 below. These criteria are consistent with those specified for HPTN 035. Participants will be screened and enrolled in the study as described in Section 3.3. Information related to participant retention and withdrawal from the study is provided in Sections 3.5 and 3.6, respectively.

3.1 Inclusion Criteria

Women who meet all of the following criteria are eligible for inclusion in this study:

• Of legal age to provide independent informed consent per local regulations and guidelines.

Note: The above-listed criterion sets a lower bound on the allowable age for study participants, but does not specify an upper bound. In order to accrue a study population at highest risk of HIV infection, individual study sites may set a site-specific upper age limit for participants based on available information about the epidemiology of HIV infection at the site, and target their study accrual efforts accordingly. All site-specific age requirements will be specified in local standard operating procedures.

- Able and willing to provide written informed consent to be screened for and to take part in the study.
- Able and willing to provide adequate locator information for study retention purposes, as defined by local standard operating procedures.
- Sexually active (defined as having had vaginal intercourse at least once in the three months prior to screening).
- HIV-uninfected at screening.

3.2 Exclusion Criteria

Women who meet any of the following criteria will be excluded from this study:

- History of adverse reaction to latex.
- History of non-therapeutic injection drug use in the 12 months prior to screening.
- Had vaginal intercourse more than an average of two times per day in the two weeks prior to screening.
- At screening:
 - Plans to travel away from the study site for more than three consecutive months in the next 12 months.
 - Plans to relocate away from the study site in the next 12 months.
 - Plans to become pregnant in the next 12 months.
- At screening or enrollment:
 - Enrolled in any other study of a vaginally-applied product.
 - Pregnant.
- At enrollment, is within 42 days of last pregnancy outcome.
- At enrollment, has a clinically apparent pelvic exam finding involving deep epithelial disruption.

Note: Otherwise eligible participants with pelvic exam finding(s) involving deep epithelial disruption may be enrolled after the finding has resolved. If resolution is documented within 30 days after obtaining informed consent for screening, screening procedures need not be repeated.

• At enrollment, diagnosed with a current STD and/or other reproductive tract infection requiring treatment according to WHO guidelines.

Note: Participants will undergo laboratory testing for chlamydia, gonorrhea, and syphilis at their screening visits, and wet mount testing for BV, candidiasis, and trichomoniasis at their enrollment visits; all results will be available at the enrollment visits. Otherwise eligible participants diagnosed at their enrollment visits with infection(s) requiring treatment per WHO guidelines (other than asymptomatic candidiasis) will be offered treatment and may be enrolled after completing treatment and all symptoms have resolved. If treatment is completed and symptoms have resolved within 30 days after obtaining informed consent for screening, screening procedures need not be repeated.

• At enrollment, has any other condition that, in the opinion of the Investigator or designee, would preclude provision of informed consent, make participation in the study unsafe, complicate interpretation of study outcome data, or otherwise interfere with achieving the study objectives.

3.3 Screening and Enrollment Process

Eligibility for the study will be assessed in a step-wise manner at the study Screening and Enrollment Visits. Although all required procedures may be completed in one Screening Visit and one Enrollment Visit, additional visits may be conducted if needed. For example, a participant may want more time to consider whether to participate in the study, may require treatment for an STD or other reproductive tract infection, or may not be able to undergo a pelvic exam due to menstruation. Regardless of the number of visits required, all screening and enrollment procedures must be completed within a 30-day period, beginning on the day the participant provides informed consent for screening. If a participant is not enrolled within 30 days after providing informed consent for screening, the screening process must be repeated.

After providing written informed consent for screening, potential study participants will be assigned an ID number and asked to provide demographic information, behavioral eligibility information, and locator information. They will undergo urine pregnancy testing and HIV and STD counseling and testing. Presumptively eligible participants will be scheduled to return for their Enrollment Visits approximately 7-14 days later, when all screening test results are expected to be available.

Note: For study screening purposes HIV infection status will be ascertained using two different rapid enzyme immunoassay tests; in the event that results from the two tests are discordant, a third test will be performed. Once a participant has enrolled in the study, follow-up HIV testing will be performed according to the algorithm in Appendix II.

At their Enrollment Visits, potential participants will be informed of their screening test results, in the context of post-test counseling, and again undergo testing for pregnancy. Those who test negative will undergo a pelvic exam with wet mount testing for BV, candidiasis, and trichomoniasis; colposcopy will be performed at selected sites. Pap smears will be performed at sites with the capacity and expertise to prepare and interpret the smears and provide appropriate follow-up care to participants with abnormal results.

Potential participants diagnosed with infection(s) requiring treatment per WHO guidelines (other than asymptomatic candidiasis) will be offered treatment at their Enrollment Visits and — provided they meet all other eligibility criteria — enrolled in the study after completing treatment and any symptoms of infection have resolved. If treatment is completed and symptoms have resolved within 30 days after providing informed consent for screening, screening procedures need not be repeated.

Similarly, potential participants with pelvic exam findings involving deep epithelial disruption observed on pelvic exam at the Enrollment Visit may be enrolled after the findings have resolved, provided they meet all other eligibility criteria. If resolution is documented within 30 days after providing informed consent for screening, screening procedures need not be repeated.

Women who meet all the study eligibility criteria will be asked to provide written informed consent to take part in the study. Those who provide informed consent will be enrolled and scheduled for their first three follow-up assessments. They will complete a baseline behavioral risk assessment and will be given instructions to contact study staff to ask questions about the study, report STD symptoms, and/or request additional HIV/STD counseling and testing between scheduled visits.

3.4 Co-Enrollment Guidelines

Participants in this study may not take part in other concurrent research studies, except for the following:

- Participants in this study may take part in microbicide acceptability studies (not involving application of vaginal products) and other ancillary studies approved by the HIVNET/HPTN 055 Protocol Co-Chairs.
- Participants who become infected with HIV may take part in HIV treatment trials.

3.5 Participant Retention

Once a participant enrolls in this study, the study site will make every effort to retain her in follow-up to minimize possible bias associated with loss-to-follow-up. It is recommended that participant retention procedures be established at each site such that loss-to-follow-up rates do not exceed the 5-6 percent average annual HIV seroincidence rate expected to be observed in the control groups of HPTN 035. As such, annual retention rates of 95 percent are targeted. Site staff are responsible for developing and implementing local standard operating procedures to achieve this goal. Components of such procedures include:

- Thorough explanation of the study visit schedule and procedural requirements during the informed consent process, and re-emphasis at each study visit.
- Collection of detailed locator information at the study Screening Visit, and active review and updating of this information at each subsequent visit.
- Use of mapping techniques to establish the location of participant residences and other locator venues.
- Use of appropriate and timely visit reminder mechanisms.
- Immediate and multifaceted follow-up on missed visits.
- Mobilization of trained outreach workers or "tracers" to complete in-person contact with participants at their homes and/or other community locations.
- Regular communication with the study community at large to increase awareness of HIV/AIDS and explain the purpose of HIV prevention research and the importance of completing research study visits.

The HPTN CORE will provide the study sites with a participant tracking database to facilitate visit scheduling and timely identification and follow-up on missed visits. The HPTN SDMC will generate weekly reports on the number and percentage of participants completing quarterly follow-up assessments. The Protocol Team as well as the HPTN Study Monitoring Committee will track retention rates closely and work with study sites as needed to take any required action to address below-target retention rates.

3.6 Participant Withdrawal

Regardless of the participant retention methods just described, participants may voluntarily withdraw from the study for any reason at any time. The site Investigator also may withdraw participants from the study in order to protect their safety and/or if they are unwilling or unable to comply with required study procedures, after consultation with the Protocol Co-Chairs, SDMC Protocol Statistician, and CORE Protocol Specialist. Participants also may be withdrawn if the study sponsors or US or local government authorities terminate the study prior to its planned end date. Study staff will record the reason(s) for all withdrawals in participants' study records.

4 STUDY PROCEDURES

See also Appendix I. Detailed instructions to guide and standardize all study procedures across sites will be provided in the study-specific procedures manual. Unless otherwise specified, the laboratory procedures listed below are performed at the local study site laboratories. See Section 8.1 for further information regarding plans to establish local laboratory capabilities for this study.

4.1 Pre-Screening

If desired, study staff may pre-screen potential study participants either on site or at off-site locations. During these interactions, study staff may explain the study to participants and ascertain presumptive eligibility, to be confirmed at an on-site Screening Visit (see Section 4.2). Pre-screening data may be recorded and stored at the study site in the absence of written informed consent from potential participants, provided the information is collected in such a manner that it cannot be linked to participant identifiers.

4.2 Screening Visit (up to day -30)

Multiple visits may be conducted to complete all required procedures if necessary. Written informed consent for screening will be obtained before any screening procedures are initiated. For potential participants who do not meet the study eligibility criteria, the screening process will be discontinued when ineligibility is determined.

4.2.1 Administrative, Behavioral, and Regulatory Procedures

- Informed consent for screening.
- Demographic information.
- Behavioral eligibility checklist.
- Locator information.
- HIV/STD counseling, condoms, other HIV prevention supplies.

4.2.2 Clinical Procedures

- Urine collection.
- Blood collection.
- Test results disclosure.
- Treatment for STD symptoms; offer of STD testing and treatment for partner(s).

4.2.3 Laboratory Procedures

- Urine pregnancy test.
- Urine ligase chain reaction (LCR) for chlamydia and gonorrhea.
- Dipstick urinalysis if clinically indicated; urine culture if dipstick is positive for leukocytes or nitrites.
- HIV serology.
- Syphilis serology.
- HSV-2 serology (at sites in Zambia only).

4.3 Enrollment Visit (day 0)

Multiple visits may be conducted to complete all required procedures if necessary. Written informed consent for study participation will be obtained before any "onstudy" procedures are initiated. For potential participants whose eligibility is not confirmed at this visit, the screening and enrollment process will be discontinued when ineligibility is determined.

4.3.1 Administrative, Behavioral, and Regulatory Procedures

- HIV/STD counseling, condoms, other HIV prevention supplies.
- Informed consent for study.
- Informed consent for specimen storage.
- Locator information.
- Behavioral risk assessment.

4.3.2 Clinical Procedures

- Urine collection.
- Blood collection.
- Focused medical history and ascertainment of current medications.
- Physical exam.
- Pelvic exam with:
 - colposcopy (at selected sites);
 - specimen collection for Gram stain;
 - wet mount for BV, candidiasis, and trichomoniasis; and
 - ecto- and endocervical cytobrush for Pap smear (at selected sites).

- Test results disclosure.
- Treatment for STDs and other infections (except asymptomatic candidiasis), when clinically indicated; offer of STD testing and treatment for partner(s).

Note: Otherwise eligible participants with pelvic exam findings involving deep epithelial disruption may be enrolled after the findings have resolved. If resolution is documented within 30 days after obtaining informed consent for screening, screening procedures need not be repeated.

Note: Otherwise eligible participants diagnosed with infections requiring treatment per WHO guidelines (other than asymptomatic candidiasis) will be offered treatment and enrolled in the study after completing treatment and all symptoms have resolved. If treatment is completed and symptoms have resolved within 30 days after obtaining informed consent for screening, screening procedures need not be repeated.

4.3.3 Laboratory Procedures

- Urine pregnancy test.
- Urine LCR for chlamydia and gonorrhea if clinically indicated.
- Dipstick urinalysis if clinically indicated; urine culture if dipstick is positive for leukocytes or nitrites.
- Gram stain assessment for BV according to the Nugent criteria at the HPTN Central Lab.
- Pap smear interpretation (at selected sites only).
- Syphilis serology if genital ulcer is observed.
- Plasma archive

Note: For participants who do not consent to long-term specimen storage and possible future research testing, archived plasma will be discarded after all protocol-required and quality assurance testing has been completed (see also Section 8.3).

4.4 Follow-up Visits

Monthly follow-up visits are scheduled throughout the study follow-up period on the monthly anniversary dates of participants' study enrollment dates. For example, for a participant enrolled on September 15, follow-up visits will be targeted to take place on October 15, November 15, December 15, etc. For participants enrolled on the last day of a month with 31 days, follow-up visits will be targeted to take place on the last day of all subsequent months (e.g., February 28, April 30, June 30, September 30, November 30). Acknowledging that it will not always be possible to complete follow-up visits on the targeted dates, visits may be completed within a four-week window around the target date (i.e., \pm 2 weeks from the target date).

For participants who do not complete scheduled visits within the allowable window, the visit will be considered "missed" and relevant case report forms will be completed to document the missed visit. However, for participants who miss visits scheduled to take place in study months 3, 6, 9, and 12, the pelvic exam and HIV counseling and testing procedures specified to take place at these visits will be conducted at the participants' next visit. Accordingly, every effort should be made to conduct participants' next visit at the study site, rather than at a community-based location. If this is not possible, an interim on-site visit in which the pelvic exam and HIV counseling and testing procedures are performed should be conducted as soon as possible after the off-site visit.

Note: Participants who become pregnant or infected with HIV during follow-up may be maintained in this study until the initiation of HPTN 035. For participants who become pregnant, follow-up procedures may be modified according to guidelines specified in the study-specific procedures manual. For example, after 24 weeks of pregnancy, quarterly pelvic exams may be discontinued and blood collection may be limited to fingersticks for HIV serology only. For participants who become infected with HIV, HIV serology will be discontinued and counseling will be tailored to primary and secondary HIV/STD prevention for infected women.

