 - Specimen collection for chlamydia and gonorrhea testing (by standard local method):
 - Quarterly.
 - Additionally when clinically indicated.
- 11. In Section 4.4.3, second bullet:
 - Urine LCR Chlamydia and gonorrhea testing by standard local method:
- 12. In Section 6.3, Tables 1 and 2:

Table 1
95% Exact Confidence Intervals for Infection Rates
Observed in a Six-Month Follow-up Period

. Infections Observed	Observed Infection Rate	95% Exact Confidence Interval
 12	1.7%	0.2-6.2%
24	3.4%	0.9-8.8%
 36	5.1%	1.8-11.2%
4 8	6.8%	2.9-13.5%
5 10	8.5%	4.0-15.7%
6 12	10.3%	5.3-17.9%

Table 2
95% Exact Confidence Intervals for Infection Rates
Observed in a Twelve-Month Follow-up Period

. Infections Observed	Observed Infection Rate	95% Exact Confidence Interval
24	1.7%	0.4-4.4%
4 8	3.4%	1.4-6.7%
6 12	5.1%	2.6-9.0%
816	6.8%	3.9-11.1%
10 20	8.5%	5.2-13.2%
1224	10.3%	6.5-15.3%

- 13. In Section 8.1, fourth bullet:
 - Urine for pregnancy testing, ehlamydia and gonorrhea LCR, dipstick urinalysis, and culture.
- 14. In Section 8.1, add seventh bullet:
 - Specimen for chlamydia and gonorrhea testing by standard local method (type of specimen dependent on local test).
- 15. In Appendix I, Schedule of Study Visits and Procedures:

urine LCR for chlamydia and gonorrhea testing by standard local method

A Study of the HIV Prevention Trials Network

Sponsored by:

Division of AIDS, US National Institute of Allergy and Infectious Diseases
US National Institute of Child Health and Human Development
US National Institute of Mental Health
US National Institute on Drug Abuse
US National Institutes of Health

Protocol Chairs:

[name], MPH, ScD Harvard School of Public Health

[name] South Africa Medical Research Council

[name] University of Miami School of Medicine

> FINAL Version 1.0 12 August 2002

TABLE OF CONTENTS

		BBREVIATIONS AND ACRONYMS	
		L TEAM ROSTER	
SCH	HEMA .		6
1	INTE	RODUCTION	7
•	1.1	Background	
	1.2	Rationale	
2	STU	DY OBJECTIVES AND DESIGN	9
	2.1	Objectives	
	2.2	Study Design	
3	STU	DY POPULATION	12
	3.1	Inclusion Criteria	12
	3.2	Exclusion Criteria	13
	3.3	Screening and Enrollment Process	14
	3.4	Co-Enrollment Guidelines	15
	3.5	Participant Retention	16
	3.6	Participant Withdrawal	17
4	STU	DY PROCEDURES	17
	4.1	Pre-Screening	17
	4.2	Screening Visit	17
	4.3	Enrollment Visit	18
	4.4	Follow-up Visits	19
	4.5	Interim Contacts and Visits	22
	4.6	Final Contact	23

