Each quarter, participants additionally will undergo a structured interview to ascertain HIV risk behaviors and receive HIV/STD pre-test, risk reduction, and post-test counseling. Participants also will undergo pelvic exams with wet mount testing for BV, candidiasis, and trichomoniasis; colposcopic evaluations will be performed at selected sites in accordance with the CONRAD/WHO Manual for the Standardization of Colposcopy for the Evaluation of Vaginal Products, Update 2000. For participants found to have a genital ulcer on pelvic exam, the ulcer will be swabbed for multiplex polymerase chain reaction (PCR) testing at the HPTN Central Lab for chancroid, herpes simplex virus 2 (HSV-2), and syphilis. Follow-up testing for chlamydia, gonorrhea, syphilis, and HIV (see Appendix II) will be performed quarterly, and additionally if clinically indicated. A sample of HIV test results will be confirmed for quality assurance purposes by the HPTN Central Laboratory.

Monthly visits other than those in which pelvic exams are scheduled may take place either on-site, in a participant's home, or at other community-based locations, depending on site capacities and site and participant preferences. If genital symptoms are reported during an off-site visit, the participant will be instructed to report to the on-site clinic as soon as possible for a pelvic exam. Other participant-initiated interim visits may occur at any time during follow-up, for example to obtain additional HIV counseling and testing.

All HIV and STD testing will be performed in the context of pre-test, risk reduction and post-test counseling. Study sites will provide this counseling in accordance with locally-accepted standards of practice and will document their counseling policies and procedures prior to study implementation for purposes of staff training, quality assurance, and study monitoring. In accordance with NIH policies, study participants must receive their HIV test results in order to remain eligible for study participation.

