4.4.2 Clinical Procedures

- Interval (i.e., since last visit) medical and menstrual history and concomitant medication review:
 - -At all visits.
- Pelvic exam with:
 - colposcopy (at selected sites);
 - specimen collection for Gram stain;
 - wet mount for BV, candidiasis, and trichomoniasis; and
 - swab for multiplex PCR if genital ulcer is observed:
 - -Quarterly.
 - -Additionally when clinically indicated.

- Urine collection:
 - -At all visits.
- Blood collection:
 - -Quarterly.
 - -Additionally when clinically indicated.
- Test results disclosure:
 - -As needed at all visits and contacts.
- Treatment for STDs and other infections (except asymptomatic candidiasis); offer of STD testing and treatment for partner(s):
 -When clinically indicated.

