4.5 Interim Contacts and Visits

Interim visits may be performed at any time during the study. Depending on the type of visit, site capacity, and site and participant preferences, interim visits may take place at the study site or at community-based locations. Interim visits may occur:

- For administrative reasons, e.g., the participant may have questions for study staff or may need to re-schedule a follow-up visit.
- For interim STD counseling and testing in response to STD symptoms.
- For interim HIV counseling and testing in response to presumed exposure to HIV.
- To provide participants with the results of confirmatory HIV test results, per the algorithm in Appendix II.
- In the event that a participant presents to the study site after having missed a scheduled visit (e.g., in response to locator/tracing efforts) on a day that does not fall within a scheduled visit window.
- To complete pelvic exam and HIV counseling and testing procedures after a missed quarterly visit.
- For other reasons at participant request.

All interim contacts and visits will be documented in participants' study records and on applicable case report forms.

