6.4.2 Secondary Analyses

Corresponding to the secondary study objectives, the following secondary analyses will be performed:

- The study accrual process will be described by tabulating the number and rate of potential participants screened for and enrolled in the study at each site, overall and by month during the accrual period. Each site's actual accrual rates will be compared to the target rates, and reasons for ineligibility for the study will be tabulated.
- The number of enrolled participants retained in the study will be tabulated for each site for the entire site-specific follow-up period as well as for each quarter in the follow-up period. Retention rates also will be calculated. The denominator for these calculations will be the total number of participants enrolled in the study at the site. The numerator will include all participants at the site who complete a scheduled visit during the interval and/or are known to have died during a previous interval. Retention rates for each site will be compared to the annual target of 95 percent.
- The demographic characteristics of persons screened for and/or enrolled in the study at each site will be described. At a minimum, the characteristics listed in Section 6.2 will be tabulated.
- The HIV risk behaviors of persons enrolled in the study at each site will be described. At a minimum, the frequency of each of the outcomes listed in Section 6.2 will be tabulated.
- The baseline prevalence for each of the genital signs and symptoms and infections listed in Section 6.2 will be computed for the enrolled study population at each site, as the total number of endpoints observed among enrollees divided by the number of participants enrolled. Appropriate 95% confidence intervals also will be computed. An incidence rate for each of the genital signs and symptoms and infections listed in Section 6.2 also will be computed for each study site, as the total number of endpoints observed divided by the total number of person-years of follow-up. Confidence intervals will be calculated based on Poisson distribution assumptions.

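### After a missed quarterly visit the protocol requires only the pelvic exam and HIV testing to be made up, so chlamydia, gonorrhea and syphilis incidence may be modestly understated and risk-behavior data for that quarter may be missing

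*Supplement*

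**What the plan says.** Section 4.4 provides that, after a missed visit at month 3, 6, 9 or 12, "the pelvic exam and HIV counseling and testing procedures specified to take place at these visits will be conducted at the participants' next visit". If that next visit cannot be on site, "an interim on-site visit in which the pelvic exam and HIV counseling and testing procedures are performed should be conducted as soon as possible". Section 4.5 lists the same purpose among the reasons for an interim visit: "To complete pelvic exam and HIV counseling and testing procedures after a missed quarterly visit". It lists STD testing at interim visits separately, with a different trigger: "For interim STD counseling and testing in response to STD symptoms".

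The quarterly schedule is wider than those two items. Section 2.2 states: "Follow-up testing for chlamydia, gonorrhea, syphilis, and HIV (see Appendix II) will be performed quarterly, and additionally if clinically indicated". The structured risk interview is also quarterly (Sections 2.2 and 4.4.1).

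In Section 4.4.2 the pelvic exam includes a Gram stain specimen, "wet mount for BV, candidiasis, and trichomoniasis; and" a swab if an ulcer is seen. The Letter of Amendment (item 10) adds a separate quarterly entry to that section, "Specimen collection for chlamydia and gonorrhea testing (by standard local method", and leaves the catch-up rule as it was. Syphilis serology is its own quarterly entry in Section 4.4.3.

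For the analysis, Section 6.4.2 defines the incidence of each listed sign or infection "as the total number of endpoints observed divided by the total number of person-years of follow-up".

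**The concern.** Estimating the incidence of nine genital conditions and describing HIV risk behaviors are stated secondary objectives. All nine incidence rates use the same estimator, but the catch-up rule treats them differently. Conditions found at the pelvic exam are measured at the make-up visit. Chlamydia, gonorrhea and syphilis need not be, and neither does the interview.

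If a quarter goes untested but its person-time stays in the denominator, the rate is biased downward, by more where more quarterly visits are missed. The retention table would not show this, because Section 6.4.2 counts a woman as retained if she completes any scheduled visit in the interval. Women who miss visits may also differ in risk, so the missing interviews need not be a random subset.

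**Working it through.** **1. Which quarterly items the catch-up rule covers**

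| Item due at months 3, 6, 9, 12 | Named for make-up (4.4, 4.5) | Appendix I, other months |
|---|---|---|
| Pelvic exam, with Gram stain and wet mount | Yes | If clinically indicated |
| HIV counseling and serology | Yes | If clinically indicated |
| Chlamydia and gonorrhea tests | No | If clinically indicated |
| Syphilis serology | No | If clinically indicated |
| Behavioral risk assessment | No | Not listed |

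A woman without symptoms who misses month 3 and attends at month 4 therefore has no stated trigger for the last three rows. Her next scheduled tests are at month 6, two months after the make-up visit.

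**2. The plan's own precision figures**

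Section 6.3 gives 117 and 234 woman-years per site. These reproduce as 240 × 0.5 × 0.975 = 117 and 240 × 1 × 0.975 = 234. With the counts corrected by the Letter of Amendment (item 12), exact Poisson limits agree with Tables 1 and 2 to within 0.1 percentage point. For example, 12 infections in 117 woman-years give 10.3% (5.3-17.9%). These figures allow for retention but not for untested quarters.

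**3. Quarterly visits due per site**

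Inputs: the Section 2.2 accrual targets (20, 30, 40, 50, 50, 50), enrollment at mid-month (assumed), site closure six months after accrual ends, and no attrition. Follow-up then runs from 11.5 months for the first group to 6.5 months for the last.
- First three groups: 20 + 30 + 40 = 90 women with visits due at months 3, 6 and 9, so 90 × 3 = 270.
- Last three groups: 150 women with visits due at months 3 and 6, so 150 × 2 = 300.
- Total: 270 + 300 = 570.

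If 5%, 10% or 20% were missed, about 29, 57 or 114 sets of tests and interviews would have no required make-up. Counting six months per woman, as the 117 woman-years imply, gives 240 × 2 = 480 visits and 24, 48 or 96 sets.

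**4. Bounds against complete testing**

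Let m be the share of quarterly tests missed and not made up, and p the chance that an undetected infection persists to the next quarterly test. Over Q quarters, an infection arising in quarter q is detected with probability Σ (1 − m)(mp)^(j−q), summed over j = q to Q. The ratio of observed to true incidence is the average over q.
- p = 0: the ratio is 1 − m, that is 0.95, 0.90 and 0.80.
- p = 1, Q = 2, m = 0.10: quarter 1 gives 0.90 + 0.90 × 0.10 = 0.99, quarter 2 gives 0.90, and the mean is 0.945. For m = 0.05 and 0.20 the ratios are 0.974 and 0.88.
- p = 1, Q = 4: 0.987, 0.972 and 0.938.

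**5. Loss compared with carrying the tests forward**

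This simulation uses the follow-up times of step 3 and a first-infection hazard of 0.10 per year. Infections are either persistent or have a mean duration of 4 months. Visits are missed independently with probability m. The comparator tests one month after a missed visit if the site is still open. Loss = 1 − (detected without make-up ÷ detected with make-up).

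| Missed (assumed) | Persistent | Mean duration 4 months |
|---|---|---|
| 5% | about 2% | about 3% |
| 10% | about 4% | about 6% |
| 20% | about 9% | about 13% |

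Infections with a mean duration of 12 months fall between the two columns.

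**The case against.** The strongest reply is that Section 4.4 sets a minimum. It does not say that only those items may be done, and Section 2.2 requires the STD tests quarterly without qualification. Section 4 leaves detailed visit instructions to the study-specific procedures manual, which may well fill the gap. This stands in part: a reader might infer that the protocol forbids the make-up, or that sites will in fact omit it, and the documents support neither. They show that the make-up is not required. Sections 4.4 and 4.5 between them state the list three times, always with the same two items, and Section 4.5 keeps STD testing apart from HIV testing.

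A reader might also infer that every infection in a missed quarter is lost. That is too strong. A persistent infection or a syphilis seroconversion can be found at the next quarterly test. Cleared infections, and those where the missed visit was the last, cannot. Nor is it stated that untested person-time counts: this follows from an unrestricted denominator, and the protocol does not define STD person-time.

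The effect is also small beside other limits. With perfect attendance, quarterly testing in the same model leaves about 16% (persistent) to 41% (4-month) of infections before site closure undetected. A 2-6% relative loss on a rate of 10 per 100 woman-years is 0.2-0.6, well inside the 5.3-17.9 interval. Visit windows are four weeks wide, and Section 3.5 provides weekly reports on quarterly completion, so high missed rates are not a given. Comparison between sites is already limited by different assays and by start-up before full proficiency in non-HIV tests. All this lowers the priority. It does not remove the unequal treatment of endpoints within a site, which is a bias that a confidence interval does not describe.

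**Conclusion.** The point holds as a gap in the catch-up rule. The protocol does not require the missed quarter's chlamydia, gonorrhea and syphilis tests or risk interview to be made up, while the pelvic exam and HIV test are. If sites follow the text as written and all person-years are counted, the three incidence rates are modestly understated relative to the conditions found at the pelvic exam. Compared with carrying the tests forward, the loss is about 2-3%, 4-6% and 9-13% of detected infections at 5%, 10% and 20% missed.

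Those missed rates, the incidence of 10 per 100 woman-years, the infection durations and the one-month make-up are all assumptions. The documents give no missed-visit rate and no evidence on how adherence varies between sites. Only secondary endpoints are affected, and a reader should not extend the point to the primary HIV endpoint, which the rule protects. This is a cheap improvement of moderate to low severity.

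**What to change.** In Section 4.4, extend the items to be done at the next visit, or at the interim on-site visit, after a missed quarterly visit. The list should cover the pelvic exam, HIV counseling and testing, the scheduled chlamydia, gonorrhea and syphilis tests, and the behavioral risk assessment. Make the same change in the Section 4.5 bullet on missed quarterly visits, and check that the procedures manual agrees.

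The cost is a wording change and a slightly longer make-up visit. No measurement is added beyond those already planned for the missed quarter, and the woman is already attending for an exam and an HIV test. Where no make-up is possible, for example because the site closes first, a sentence in Section 6.4.2 on how untested intervals enter the STD denominator would deal with the remainder.
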